2 STUDY OBJECTIVES

The primary objective of this study is to investigate the comparative efficacy of the UCB infusion and the non-invasive treatments for improving the functioning of children with ASD.

A secondary objective is to determine whether there are significant differences in the safety profiles of the two treatments administered

In addition there will be an evaluation of the structural changes in the CNS of the children with ASD, done by MRI

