3 STUDY PLAN AND PROCEDURES

3.1 Study design

This is a twelve months long, open-label, crossover study to evaluate the comparative efficacy and safety of UCB versus non-invasive treatments in children with ASD. Each participant will receive both treatments in a random sequence.

The UCB is autologous, previously harvested at the child's birth and cryopreserved in liquid nitrogen for later use.

The UCB infusion was performed at Angiomedica Hospital, [name] as main site and in two additional clinical sites: Medicover Hospital, [name], and Ponderas Academic Hospital, [name], all in Bucharest, Romania by anesthesiologist and pediatric physician, based on the Duke protocol.

Prior to UCB infusion, HLA typing of the child will be performed at the National Institute of Hematology, as well as the HLA typing of the UCB prior to thawing – for positive identification. During this time the UCB collection will be kept in liquid nitrogen for a maximum of 72 hours, after which thawing and preparing of the UCB for infusion will be performed by [name]; the thawing is done in optimal conditions for preserving simultaneously both sterility and viability of the cryogenated cells - the Vita 34 or Rubinstein protocols; testing for viability will be done with Trypan Blue and flowcytometry. Choosing optimal conditions is based upon the minimum number of processing steps necessary (fewest number of centrifugations and shortest time of processing, with best recovery of various stem cells) and ensuring sterility.

The non-invasive treatment combination is prescribed by the study investigator after the three questionnaires are answered and an evaluation by child therapist/psychologist is performed independently. This treatment is

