4.3 Specific detail on measurements

4.4.1 Adverse events

An adverse event is the development of an undesirable medical condition - e.g. symptoms or abnormal results of an investigation - or the deterioration of a pre-existing medical condition (not relevant in this study). AE's will be collected by means of a standard question: "Have you had any health problems since the previous visit?" AE's will be recorded at every visit. Spontaneously reported AE's and/or observed AE's and the subject's response to this question will be recorded on the AE form with information about seriousness, action taken, date of onset and recovery, maximum intensity and outcome. The subjects will be asked to assess the intensity of the reported Adverse Event according to the following scale:

Mild = awareness of sign or symptom, but easily tolerated
Moderate = discomfort sufficient to cause interference with normal activities
Severe = incapacitating, with inability to perform normal activities.

A Serious Adverse Event is an adverse event occurring during any phase of the study and at any dose of the investigational product or placebo, which fulfils one or more of the following criteria:

- Results in death;
- Is immediately life-threatening;
- Requires in-subject hospitalization;
- Results in persistent or significant disability or incapacity.

The causality of Serious Adverse Events (i.e. the relationship to study treatment) will be assessed by the investigators, who in completing the relevant Case Report Form must answer ‘yes’ or ‘no’ to the question “Do you consider that there is a reasonable possibility that the event may have been caused by the study medication?” The following factors should be considered when deciding if there is a “reasonable possibility” that an Adverse Event may have been caused by the investigational product.

- Time course of events and exposure to suspect drug – did the AE occur in a reasonable temporal relationship to the administration of suspect drug?
- Dechallenge experience – did the AE resolve or improve on stopping or reducing the dose of the suspect drug?
- Rechallenge experience - did the AE reoccur if the suspected drug was reintroduced after having stopped?
- Laboratory tests – has a specific laboratory investigation confirm the relationship?
- No alternative cause - the AE cannot be reasonably explained by another aetiology such as an underlying disease (not previously present), other drugs or environmental factors.

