6. ETHICS

6.1 Ethics review

The final study protocol, including the final version of the Informed Consent Forms, must be approved in writing by The Ethics Committee before enrolment of any subject into the study. The Principal Investigator (Clinical Trial Manager) is responsible for informing the IEC of any serious adverse events (SAE) and amendment to the protocol as per regulatory requirement.

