Annex 6 – Infusion protocol

Form Version 1 Printed from StemCare QMS 2019-01-22 Page 1 of 1 CBU Infusion Procedures

Principle

At the transplant center, the cryoprotected cord blood unit (CBU) is stored in the vapor phase of liquid nitrogen until the day of transplant, when it is thawed and washed in dextran / albumin, a process which increases cell viability and removes approximately 90% of the DMSO/dextran cryoprotectant. The washed cells are resuspended in dextran/albumin and transported to the patient's bedside in a labelled transplant bag for infusion.

The unit is infused into the patient's blood via the central venous catheter over 2-30 minutes. Every effort should be made to be sure that all the cells in the transplant bag and IV tubing are delivered to the patient, maintaining a closed system during the infusion.

Specimen

Thawed and washed cells from a cryopreserved cord blood unit (CBU) in a labelled transplant bag.

Reagents

500 ml bag of Normal Saline

Supplies

Y-infusion set

IV extension tubing

Blood filter, 170-260 microns

Procedure

- 1. Verify that the patient is stable and has received premeds for transplant.**
- 2. Verify that the transplant bag label matches patient identifiers via institutional procedures.**
- 3. Examine transplant bag to be sure that cells are in solution and that large clumps are not present in the bag. If clumps are present, prepare to use blood filter in infusion set-up.**
- 4. Close all clamps on the tubing on the Y-infusion set and blood filter.**
- 5. Spike one arm of the Y-infusion set into the bag of normal saline.**
- 6. Connect extension tubing to the distal arm of the Y-infusion set.**
- 7. Prime all tubing with normal saline.**

- 8. Spike the other arm of the Y-infusion set into the transplant bag.**
- 9. Connect the distal end of the extension tubing to the patient's central venous catheter.**
- 10. Open the clamps between the transplant bag, the extension tubing, and the patient's central line and allow cells to infuse into the patient's blood.**
- 11. Rinse residual cells in the transplant bag and tubing. After all cells have dripped out of the transplant bag, close the clamps on the extension tubing and Y-set connected to the transplant bag. Open the clamps between the normal saline bag and transplant bag and allow approximately 25 cc of saline to run into the transplant bag. Close the clamps between

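### The serious adverse event definition omits prolonged hospitalisation and medically important events, so some significant events can be classed as non-serious, possibly more often after cord blood than on treatment B

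*Combined protocol and SAP*

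**What the plan says.** Section 4.4.1 calls an adverse event serious if it meets at least one of four criteria:

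1. "Results in death"
2. "Is immediately life-threatening"
3. "Requires in-subject hospitalization"
4. "Results in persistent or significant disability or incapacity"

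The list ends there, with no catch-all. The synopsis, the other sections and the annexes add nothing to it.

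Two procedures hang on the classification. In 4.4.1 the investigator's yes/no causality question is set for SAEs. In 6.1 the Principal Investigator "is responsible for informing the IEC of any serious adverse events (SAE", in line with regulatory requirements.

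The two treatments are given in different settings. Section 3.1 says "The UCB infusion was performed at Angiomedica Hospital" as main site and names two further hospitals, with an anaesthesiologist and a paediatric physician giving the infusion. Annex 6 describes bedside infusion "via the central venous catheter over 2-30 minutes". Treatment B is prescribed to the parents (4.2, Visit 1), and its intake is recorded in a diary kept at home (section 4.4, daily diary).

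Section 2 states: "A secondary objective is to determine whether there are significant differences in the safety profiles of the two treatments administered".

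**The concern.** A definition made of listed criteria classifies only what the list covers. Two kinds of event fall outside it or on its edge: one that lengthens a stay already under way, and one that needs real intervention but is dealt with without admission. Annex 5 itself names hazards that could produce such events, namely adverse effects of the cryoprotectant and bacterial contamination from a cracked or leaking bag.

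If such an event is classed as non-serious, nobody has to answer the causality question about it, and the SAE route to the ethics committee does not open. The participants are children aged 3 to 7, so that matters whatever the comparison shows.

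There is also a comparative side. The third criterion turns on hospitalisation, and one treatment is given in a hospital while the other is taken at home. A seriousness label that depends partly on where the child happens to be is a weak basis for comparing safety profiles, which is the trial's secondary objective.

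**Working it through.** No arithmetic applies: the protocol states no SAE rate and no figure built on one. The check is to apply the four criteria to one kind of event in each setting.

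Take an event that needs medical care, is not immediately life-threatening and leaves no lasting disability. Criteria 1, 2 and 4 are then not met, and everything rests on criterion 3.

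| Situation | Criterion 3 as written | With a prolongation item and a medically important item |
|---|---|---|
| Treatment B at home, child admitted | Met: SAE | SAE |
| Treatment B, treated at home or as an outpatient | Not met: non-serious | SAE if judged medically important |
| Cord blood as a day case, reaction leads to admission | Met: SAE | SAE |
| Cord blood as a day case, reaction managed on site | Not met: non-serious | SAE if judged medically important |
| Cord blood in an admitted child, stay extended | Depends on how the assessor reads the criterion | SAE |
| Cord blood in an admitted child, managed within the planned stay | Not clearly met: non-serious | SAE if judged medically important |
| Cord blood, problem appears after going home, child admitted | Met: SAE | SAE |

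Four things follow.

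- The missing medically important item affects both treatments (rows 2, 4 and 6).
- The missing prolongation item matters in row 5. That row arises from cord blood treatment only if infused children are formally admitted.
- Admission status is not stated. Annex 5 speaks of the patient's room and Annex 6 of the bedside, which suggests admission. Against that, the infusion lasts 2 to 30 minutes and is given at a study visit, which fits a day case. With three hospitals, practice may differ between sites.
- An event that stays non-serious is not lost. Under 4.4.1 the form still records seriousness, action taken, dates of onset and recovery, maximum intensity and outcome, and 5.2 lists adverse events individually by treatment group. What is lost is the trigger for the causality question and for ethics committee notification.

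**The case against.** The strongest defence has four parts.

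**Criterion 3 does not say new.** An event that keeps a child in hospital can be read as requiring hospitalisation. This is a fair reading, so it would be wrong to say that the protocol excludes a prolonged stay. But the text leaves the choice to each assessor in an open-label trial at three hospitals, and it does nothing for events managed on site.

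**Other provisions cover the gap.** Section 6.2 invokes Good Clinical Practice and applicable regulation, and 6.1 ties reporting to regulatory requirements. The factors for judging causality in 4.4.1 are worded for adverse events generally, and a safety monitor reviews the data. These soften the consequence. They do not replace the explicit four-item definition that investigators would apply, and the mandatory yes/no question is still set for SAEs.

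**The home comparator is not automatically counted.** A reader might infer that equally severe treatment B events would all be SAEs, so that only cord blood is under-counted. The documents do not support that. A reaction treated on the spot in hospital could also be treated at home or as an outpatient, and would be non-serious there too.

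**No SAE comparison exists to be distorted.** A reader might also infer that a few missed events would reverse the safety result. Section 5.2 plans listings. The synopsis promises summary statistics for safety variables and names a chi-square test for categorical variables in general, without mentioning SAEs. Suppose, purely as an assumption, that 3 of 25 children had such an event after cord blood and none on treatment B. The exact paired two-sided p would be 2 × 0.5³ = 0.25, so even correct counting would not establish a difference.

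The last two parts stand and limit the claim. The first two do not remove it.

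**Conclusion.** The point holds as a flaw in a stated rule. Followed as written, the definition in 4.4.1 can leave a significant event non-serious, and so outside the causality question and the ethics committee notification specified for SAEs. That much rests on the text alone.

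That the gap weighs more on cord blood is possible but conditional. It depends on whether infused children are admitted and on how each hospital reads the third criterion, and the documents settle neither. The likely direction is towards fewer events labelled serious after cord blood, but its extent is unknown.

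No size can be given. The protocol states no event rate for either treatment, and an assumed count would show only what had been assumed. Immediately life-threatening, fatal or disabling events are classified the same way under both treatments, so the gap concerns events of intermediate gravity.

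**What to change.** In 4.4.1 and on the SAE form:

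- change the third criterion to 'requires in-patient hospitalisation or prolongation of existing hospitalisation';
- add a fifth criterion for a medically important event in the investigator's judgement, including one that needs intervention to prevent one of the listed outcomes;
- state that planned hospital attendance for the infusion is not itself an SAE;
- state that the same wording applies to both treatments and at all three infusing hospitals.

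The fourth criterion needs no change. If children have already been treated, the recorded action taken, dates and outcome may allow existing adverse events to be re-reviewed under the revised definition.

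The change is a few lines of text and alters no treatment, visit or sample size. It has two costs. A few more events will be reported as serious. The new criterion also rests on judgement in an open-label trial where, under 3.3.4, the Principal Investigator is directly responsible for a stage of cord blood preparation, so classification could itself vary with treatment. Recording a short reason for each such classification would let the safety monitor check consistency.

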Final Protocol:	June 2019	Clean File:	June 2019
Ethics Approval:	January 2019	Statistical analysis:	
Clinical Phase:		Study Report:	
OBJECTIVES:	To compare the safety and efficacy of administering intravenous autologous cord blood versus personalized noninvasive treatments to children with developmental disorders of the autistic spectrum		
STUDY DESIGN:	An open-label, pilot crossover study over a 12-month period. Participants will be screened and randomized at Visit 0 and at visit V1 will be receiving either intravenous umbilical cord blood or noninvasive treatment. At V2, at 2 months after V1, the other treatment is administered and subsequently the child will be evaluated by questionnaires and child therapist. Parents will report adverse events and complete the M-CHAT, Q-CHAT and CAST questionnaires. Modifications on these questionnaires will be analyzed statistically as a quantitative measure of child's improvement.		
SUBJECTS:	
Inclusion criteria Males and females between 3 and 7 years of age:
 
 • parents informed of the nature of the study and will give written informed consent, • have body weights between 10-30 kg, • have no clinically significant abnormal values on hemoleucogram during screening, • be on no regular medical treatment • have no known allergies to treatments 
Exclusion criteria
 
 • Any genetic or metabolic disease or condition which might compromise the haematopoietic, renal, endocrine, pulmonary, central nervous, cardiovascular, immunological, dermatological, gastrointestinal or any other body system. • History of allergic conditions – asthma, urticaria, eczema. • History of autoimmune disorders 		

	
 • Intake of any medication within 14 days before start of the study • Presence of significant abnormal hemoleucogram results during screening.
TREATMENT TO BE EVALUATED	
Active Treatment A: Autologous umbilical cord blood administered intravenously as single treatment .
 
Active Treatment B: Personalized daily treatment following evaluation with a combination of intranasal Oxytocin; Curcumin; Lecithin, Piracetam, Tecfidera; PQQ; Magnesium citrate and vitamin B6

DURATION OF STUDY	12 months

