1.2 Study Rationale

Even though it is a recent development, UCB has had the best results so far in treating children with ASD and its results recommend it for treatment to any child with ASD and who had UCB collected at birth. Two important questions arise:

- what other treatment can be recommended to the ASD children without UCB collected at birth, and with what comparative efficacy, and
- being a one-time intervention, can we improve/add to UCB infusion other substances which have a very good safety profile (well tolerated) and at least theoretically have a benefit in improving neuronal function?

To begin to answer these questions we have devised an open-label clinical study with a crossover design (all children receive both treatments, albeit in a different sequence).

One important novelty with our study is that the treatment to which UCB is compared is not the same to all children, but is individually tailored to address specifically the most important problems the child has (inflammation, anxiety/social avoidance, myelination, global delay, etc)

Based on the results of the testing with the M-CHAT-R, Q-CHAT and CAST questionnaires and the evaluation from child psychologist, a recommendation for treatment will be made.

The noninvasive treatment consists of a combination of at least two substances from the

following: Oxytocin 10 UI/day intranasally, Magnesium citrate and vitamin B6 ½ cp qd, pironoquinolinquinone (PQQ) 20 mg qd, Lecithin 1000 mg qd, Curcumin 500 mg qd. The specific treatment components will be recommended and administered according to the criteria below, after performing all the tests (imagistics, labs, questionnaires) which can suggest a deficiency on one or more of the following directions:

- inflammatory problem (IP markers on labs, white matter changes, diffuse or no specific modification on MRI)
- myelination (MRI changes),
- anxiety/social avoidance (questionnaires),
- severe developmental delays in cognition, logic, verbalization

1. ***Curcumin 250 mg bid*** will be included in the child's regimen if the imagistics (MRI/CT scan) and/or laboratory values (IP) suggest the presence of an inflammatory status, either in the CNS (white matter modifications on the brain scan) or systemic (abnormal values in the Inflammatory Panel done from blood);

2. ***Oxytocin 10 UI/day*** via intranasal administration will be administered if a social-communication deficit is clearly shown at evaluation

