There would not be a “reasonable possibility” of causality if none of the above criteria apply or where there is evidence of exposure and a reasonable time course, but any dechallenge is negative or there is another more likely cause of the AE.

In this study the Adverse Events will be noted from the interview at the time of visit and from the daily input in the diary.

4.4.2 12- Lead ECG

Standard 12-lead ECGs will be performed at the indication of the anesthesiology doctor if necessary.

The Bioclinica Laboratory will perform all the clinical laboratory investigations.

The samples will be processed and shipped as per instructions of the pathology laboratory.

For all laboratory investigations the investigator will receive actual printouts of the data from the Laboratory. A signed original printout will be attached to the CRF and a copy thereof will be filed in the subject file. The reference ranges will be provided in the clinical trial manual (investigator’s file) together with the descriptions of the laboratory methods used. The laboratory will provide normal ranges on each report to ease the investigator’s assessment.

As part of the overall safety monitoring plan, the safety monitor ([name]) will also assess the data, particularly those falling outside the normal range.

The blood samples will always be taken before the first trial medication dose for that day is taken. The blood samples will be collected in tubes labeled with the following information: patient name; test type (HLA, biochemistry, hematology, flowcytometry); blood sample number (visit 2, 3,4 or 5) and sampling time.

Blood samples will be handled according to the protocols for testing of the respective laboratories

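### Section 4.4.1 lets a negative dechallenge alone rule out causality: lasting serious harm on treatment B is literally classed as unrelated, and after a completed UCB infusion the rule can be read either way

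*Combined protocol and SAP*

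**What the plan says.** Section 4.4.1 states that "The causality of Serious Adverse Events (i.e. the relationship to study treatment) will be assessed by the investigators", who answer a yes/no question on the CRF. It lists five factors to consider: time course, dechallenge, rechallenge, laboratory confirmation and absence of another cause. Dechallenge is put as the question "did the AE resolve or improve on stopping or reducing the dose of the suspect drug", and rechallenge as "did the AE reoccur if the suspected drug was reintroduced after having stopped". No not-applicable answer is described for either.

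The same section then says when there is no reasonable possibility of causation. One case is that none of the factors apply. The other is "evidence of exposure and a reasonable time course, but any dechallenge is negative or there is another more likely cause of the AE".

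One of the four criteria for a serious event is "Results in persistent or significant disability or incapacity".

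The two treatments differ in how they can be withdrawn:

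- Treatment B is taken daily for 6 weeks and followed by 2 weeks without treatment (section 3.1.1).
- Treatment A is described in the synopsis as "Autologous umbilical cord blood administered intravenously as single treatment" and in the Study Rationale as "being a one-time intervention". Annex 6 adds: "The unit is infused into the patient's blood via the central venous catheter over 2-30 minutes".

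**The concern.** A positive dechallenge supports causation. A negative one is weak evidence against it, and for permanent injury it is no evidence at all, because such an injury persists whatever caused it. The exclusion sentence nevertheless lets a negative dechallenge outweigh fitting exposure and timing. Permanent disability is itself a reason for calling an event serious, so some of the events that must be judged are ones for which this test is uninformative.

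The wording also assumes a treatment that can be withdrawn. That describes B. It does not describe UCB once the bag is empty, and the section gives no separate instruction for that case.

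What is at stake is whether the causality recorded for a serious event is right and is reached in the same way by different investigators. The trial is small and open-label, with a stated secondary objective of comparing the two safety profiles. A reader of the report will look at each serious event and at the investigator's causality answer beside it.

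**Working it through.** The plan gives no figure on this point, so there is none to reproduce. The check applies the exclusion rule to each possible dechallenge result.

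**Step 1: the rule.** From section 4.4.1, causation is ruled out if (none of the factors apply) OR (exposure and time course fit AND (dechallenge is negative OR another cause is more likely)).

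**Step 2: apply it.** Take a serious event with fitting exposure and time course and no more likely cause.

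| Dechallenge result | Ruled out? |
|---|---|
| Positive | No |
| Negative | Yes |
| Not done or not possible | No |

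The dechallenge entry alone decides the answer.

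**Step 3: treatment B.** B is stopped after 6 weeks, so a real dechallenge takes place. A lasting injury has not improved on stopping and falls in the second row, ruled out. This follows from the text without interpretation.

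**Step 4: UCB.** The infusion lasts 2 to 30 minutes. A reaction in that window could be followed by stopping, so dechallenge is possible there. After completion nothing remains to stop or reduce, and no second infusion is planned. Of the five factors, dechallenge and rechallenge drop out, leaving 5 − 2 = 3: time course, laboratory confirmation and alternative cause. An investigator who answers the dechallenge question for a persisting event may write no (second row, ruled out) or treat it as not done (third row, not ruled out). The documents do not choose between these.

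**Step 5: scale, for illustration only.** The plan does not commit to reporting a rate of related serious events. If such a rate were quoted, assume 25 treated children (the section 3.2 minimum) or 40 (the synopsis optimum), and one related serious event recoded as unrelated. Intervals are exact (Clopper-Pearson) 95%; the upper limit for 0 of n is 1 − 0.025^(1/n).

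| Treated | One related event | After recoding |
|---|---|---|
| 25 | 1/25 = 4.0% (0.1% to 20.4%) | 0/25 = 0% (0% to 13.7%) |
| 40 | 1/40 = 2.5% (0.1% to 13.2%) | 0/40 = 0% (0% to 8.8%) |

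One coding decision is enough to move the count from one to none. How many such events would occur cannot be derived from the documents.

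**The case against.** The strongest objection concerns UCB. The clause speaks of any dechallenge being negative, which most naturally means a dechallenge that took place. If none took place, the exclusion is not triggered. A reader might infer that lasting harm after UCB will be classed as unrelated. The documents do not support that: it happens only if an investigator codes persistence as a negative dechallenge. What stands is that the text does not settle the coding. The objection does not help treatment B, where a real dechallenge occurs.

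A reader might also infer that the rule distorts the safety comparison or keeps events from the ethics committee. The documents do not support that either. Section 4.1 defines the endpoint by type and frequency of adverse events. Section 5.2 lists events individually per treatment group with no causality filter. Section 6.1 has the ethics committee told of any serious event. No planned analysis uses the causality answer. This part of the objection stands in full and limits the point to what is recorded about causality.

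Third, judgement is retained: the factors are to be considered, and the AE form captures onset, recovery, action taken and outcome, so an event can be re-judged later. That is fair, but the exclusion sentence is written as a conclusion, not as one more factor to weigh, so it directs the judgement.

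Finally, the yes/no assessment is stated for serious events only. That is correct, and non-serious events that persist are outside this point.

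**Conclusion.** The point holds within narrow limits. As written, section 4.4.1 gives a wrong default for irreversible serious events on treatment B, and an indeterminate one for serious events that persist or appear after a completed UCB infusion. It does not show that UCB harm in particular is hidden: read literally, the clause bites on B, and reaches UCB only through an unsettled coding choice. Nor does it show that any event goes unlisted or unreported.

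The size is the recorded causality of whichever serious events are lasting. That number is unknown and may be zero, but in a trial of 25 to 40 children a single event would matter to the reader. The conclusion assumes that investigators apply the exclusion sentence as written, and that no instruction elsewhere, for example in CRF guidance that is not part of the documents, overrides it. The change is worth making because a stated rule can give the wrong answer and correcting it costs very little.

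**What to change.** In section 4.4.1:

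1. Remove negative dechallenge as a sufficient ground for answering no. Keep it as one factor to weigh.
2. State that persistence of an event does not by itself rule out causality, for either treatment.
3. State that dechallenge and rechallenge are not applicable once the UCB infusion is complete, and that such events are judged on time course, laboratory confirmation and alternative cause.

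If the CRF has fields for dechallenge and rechallenge, add a not-applicable option. The form is not in the documents, so whether this is needed is unknown.

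The cost is a few sentences and possibly one form change. The downside is that a few more serious events may be classed as related. Nothing in the listings, the notification of serious events or the treatment schedule has to change.
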